4.2.2 Secondary Study Endpoints

Acceptability will be assessed using patient exit interviews (PEIs) conducted right after the dental visit is completed.

CONFIDENTIAL

This material is the property of the NYU School of Medicine and Langone Medical Center. Do not disclose or use except as authorized in writing by the study sponsor

Interventional Template Version: 28 APR 2017

Acceptability data collection.

Research staff will conduct a brief exit interview with 5 patients at each of the 6 FHC dental clinics with language interpretation services available regarding the acceptability of the intervention. We developed five statements on patient satisfaction with the intraoral cameras and the overall tele-mentoring intervention that will constitute the PEI. Patients will be asked the extent to which they agree with each statement (e.g., “Dentists should discuss with me ways to prevent and screen for oral cancer.”) (strongly agree, agree, disagree, strongly disagree). The acceptability criterion of the intervention will be that 80% or more of patients rate all five administered acceptability questions as “strongly agree” or “agree.” We will evaluate acceptability as described above for feasibility.

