Using a mixed-methods approach, we will evaluate and enhance the feasibility and acceptability of integrating a tele-mentoring component into the identification of oral lesions at the 6 FHC dental clinics. This will be achieved through:

1. Administering provider surveys (n=12) that consist of a checklist of 10 key components of the intervention based on process, and asking the dental provider subjects at each of the 6 FHC dental sites if each one was covered.
2. Conducting semi-structured interviews (n=6) with dental resident subjects at each of the 6 FHC sites to assess specific barriers to sustaining the intervention and strategies for addressing these barriers to facilitate integration of the intervention into the routine workflow of the dental clinics. The interviews will be informed by the Consolidated Framework for Implementation Research (CFIR)¹ and the Implementation Outcomes Framework (IOF).²
3. Administering brief exit interviews (n=30) with patient subjects at each of the 6 FHC dental sites regarding the acceptability of the intervention. The survey will assess patient satisfaction with the use of intraoral cameras at chairside to screen for and refer patients with oral lesions and identification of these oral lesions via tele-mentoring with an oral pathology expert ([name]).

Impact: If this pilot study proves successful, NYU Langone Health is well-equipped with both teaching and organizational expertise in faculty development activities, as well as the existing NYU Langone Dental Medicine national network of video-teleconferencing and web-based educational technology, to scale-up the proposed oral pathology asynchronous tele-mentoring educational program for the teaching of dental educators and residents, with the ultimate goal of improving patient care.

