3.2 Secondary Objectives (if applicable)

To assess the acceptability of the asynchronous tele-mentoring pilot intervention to adult dental patients.

CONFIDENTIAL

This material is the property of the NYU School of Medicine and Langone Medical Center. Do not disclose or use except as authorized in writing by the study sponsor
Interventional Template Version: 28 APR 2017

4 Study Design and Endpoints

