4.1 Description of Study Design

This one-year pilot study is composed of 2 parts:

- During months 1-6, we will complete the installation of the intraoral cameras in the dental operatories at FHC and design the Dentrix EHR screens for entering the information and tracking the involved steps of the tele-mentoring intervention. Dentist and resident subjects at all 6 FHC dental sites will then be trained by [name] and [name] to use the intraoral cameras to take photographs of oral lesions and place them in the Dentrix EHR, along with descriptions of the lesions.
- During months 6-12, dentist and resident subjects will begin screening eligible patients for oral lesions and place photographs and descriptions of any found lesions in the Dentrix EHR, along with an initial dummy code entry. For each patient with a detected lesion, [name] will then review the Dentrix EHR chart and the uploaded photograph(s) of any lesion(s) found and place his observations in the Dentrix EHR. Next, [name] will discuss his findings with the involved dental faculty member / dental resident via secure NYU Langone Health e-mail. The dental provider will then enter an apt comment in the Dentrix EHR, using the following template: "Reviewed entry and contacted patient. Follow-up appointment needed / not needed (+ date) for an appointment on (date)." A second dummy code entry will then be placed in the patient chart in the Dentrix EHR. Once a week, [name] will receive a Dentrix EHR report with the 2 affiliated dummy code entries for the tele-mentoring pilot study, thus assuring that entries are made for both codes, and the loop is closed. We will also pilot feasibility and acceptability of the intervention by completing provider surveys, semi-structured interviews with dental residents, and patient exit interviews.

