6.2 Study Procedural Intervention(s) Description

The tele-mentoring intervention involves training dental faculty members and residents to use intraoral cameras to take photographs of oral lesions and place them in the Dentrix electronic health record (EHR), along with descriptions of the lesions. This information will then be sent via Dentrix EHR to [name], the Director of Oral Pathology at NYU Langone Hospital – Brooklyn, and an initial dummy code entry will be placed in the Dentrix EHR. For each patient with a detected lesion, [name] will then review the Dentrix EHR chart and the uploaded photograph(s) of the lesion(s) found and place his observations in the Dentrix EHR. Next, [name] will discuss his findings with the involved dental faculty member / dental resident via secure NYU Langone Health e-mail. The dental provider will then enter an apt comment in the Dentrix EHR, using the following template: “Reviewed entry and contacted patient. Follow-up appointment needed / not needed (+ date) for an appointment on (date).” A second dummy code entry will then be placed in the patient chart in the Dentrix EHR. Once a week, [name] will receive a Dentrix EHR report with the 2 affiliated dummy codes for the tele-mentoring pilot study, and assure that entries for both codes are entered, and the loop is closed.

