7.1 Study Procedures/Evaluations

7.1.1 Study Specific Procedures

The protocol for the tele-mentoring study was designed by Drs. [name] and [name], and is provided on the following page. This workflow will be refined based upon the results of the planned feasibility and acceptability testing. All study activities will take place in the 6 FHC dental clinics and private offices of NYU Langone Dental Medicine in Brooklyn, NY. The PEIs with patient subjects and the feasibility checklists with provider subjects will take 10-15 minutes to complete. The semi-structured interviews with dental resident subjects will take 30-45 minutes to complete, and will be digitally recorded and transcribed. The transcriptions will be stored in a secure REDCap database. The digital files will be deleted once they are transcribed. No identifying information will be recorded.

A2. Data Collection

[figure not shown]
Feasibility of the integrated intervention will be assessed through dental provider surveys and semi-structured interviews. The dental provider survey, which consists of a checklist of 10 key components of the tele-mentoring intervention to be implemented, will be completed by 2 dentists at each of the 6 FHC dental clinics (n=12) after screening at least 1 patient subject for oral cancer using an intraoral camera, as per the tele-mentoring protocol. Furthermore, after we have reached our target of 30 patient participants (5 patient participants at each of the 6 FHC dental sites), we will engage 6 dental residents (1 at each of the 6 FHC dental clinics) in a semi-structured interview to assess specific barriers they have encountered to sustaining the intervention and strategies for addressing those barriers to facilitate integration of the tele-mentoring intervention into the routine workflow of the dental clinics.

Acceptability of the integrated intervention will be assessed through brief patient exit surveys. Consented participants will be asked to complete a brief patient exit survey at the end of their dental appointments after being screening for oral cancer lesions using an intraoral camera.

The protocol for the tele-mentoring study is provided below:

CONFIDENTIAL

This material is the property of the NYU School of Medicine and Langone Medical Center. Do not disclose or use except as authorized in writing by the study sponsor
Interventional Template Version: 28 APR 2017

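### The exit interview comes before the pathologist's review and feedback, so it supports a narrower acceptability claim than the plan makes, and the acceptability criterion is stated in two versions

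*Combined protocol and SAP*

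**What the plan says.** All references are to the combined protocol and SAP.

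**When patients are asked.** Section 4.2.2: "Acceptability will be assessed using patient exit interviews (PEIs) conducted right after the dental visit is completed". Section 7.1.1 agrees: "Consented participants will be asked to complete a brief patient exit survey at the end of their dental appointments", after the camera screening. No second patient measurement is described.

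**When review and feedback happen.** Sections 3, 4.1 and 6.2 give the same order. The photograph and description go into the EHR. The pathologist then reviews chart and image, records observations and e-mails the provider. This is done "For each patient with a detected lesion". Only after the e-mail does the patient step appear: "The dental provider will then enter an apt comment in the Dentrix EHR, using the following template". The template records that the patient was contacted and whether follow-up is needed. A weekly report checks that the loop is closed.

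**What the result is said to show.** The secondary objective in section 3.2 is "To assess the acceptability of the asynchronous tele-mentoring pilot intervention to adult dental patients". Section 3, item 3, includes satisfaction with "identification of these oral lesions via tele-mentoring with an oral pathology expert". Section 4.2.2 describes "five statements on patient satisfaction with the intraoral cameras and the overall tele-mentoring intervention that will constitute the PEI".

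**How it is judged.** Sections 4.2.2 and 9 both require 80% or more of patients to agree or strongly agree with all five items. Section 4.2.2 then adds "We will evaluate acceptability as described above for feasibility". The feasibility method in section 4.2.1 is an average endorsement score with a 95% confidence interval, and it counts as success if the upper limit exceeds 80%.

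**The concern.** There are two separate issues.

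**Scope of the claim.** The remote review is what distinguishes this intervention from chairside photography. If patients answer before it takes place, they can say how they found the camera and what they think of remote review. They cannot report how the review, the wait or the feedback went. The plan would nonetheless report a met criterion as acceptability of the tele-mentoring intervention. That label has consequences: section 7.1.1 will refine the workflow from the acceptability results, and section 3 ties a successful pilot to scale-up.

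**Decision rule.** A point-estimate rule and a rule on the upper confidence limit are different tests. With 30 patients they can give opposite conclusions from the same data. Section 9 states only the first; section 4.2.2 states the first and then points to the second.

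**Working it through.** **1. Sequence, by type of patient**

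| Step (sections 4.1, 6.2, 7.1.1) | Lesion detected | No lesion |
|---|---|---|
| Camera screening in the visit | yes | yes |
| Exit interview at end of visit | yes | yes, as the text reads |
| Pathologist review and e-mail to provider | after photo upload | does not occur |
| Provider contacts patient | after the e-mail | does not occur |

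Three sections might have altered this order, but none moves the interview:
- 7.3.2 places use of the tele-mentoring protocol in the regular visit.
- 7.3.3 has the provider discuss next steps.
- 5.5 gives participation of 1-2 days including follow-up.

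That lesion-free patients are interviewed follows from four sections. Section 4.1 screens eligible patients and uploads any lesions found. Section 7.3.1 decides eligibility from medical and medication history. Section 7.3.2 describes the camera screening as a later step. Section 7.1.1 gives the exit survey to consented participants with no lesion condition.

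**2. How many patients the timing can affect**

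Inputs: n = 5 × 6 = 30 (section 5.6). Lesion frequency L is an assumption; the documents give none.

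Expected lesion patients = 30 × L. Chance of none = (1 − L)^30.

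| Assumed L | Expected lesion patients | Chance of none |
|---|---|---|
| 5% | 1.5 | 21.5% |
| 10% | 3 | 4.2% |
| 20% | 6 | 0.1% |

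**3. The two criteria**

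The plan's own rule in section 9: 0.80 × 30 = 24 patients. The exact (Clopper-Pearson) 95% interval for 24/30 is 61.4% to 92.3%.

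The upper-limit rule, applied to the proportion of patients. The documents name no interval method, so two are shown:

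| Patients agreeing on all five items | Exact upper limit | Wilson upper limit |
|---|---|---|
| 18/30 (60%) | 77.3% | not needed |
| 19/30 (63%) | 80.07% | 78.1% |
| 20/30 (67%) | not needed | 80.8% |

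The rule is first met at 19/30 (exact) or 20/30 (Wilson). Results of 20, 21, 22 or 23 of 30 therefore pass it under either interval and fail the section 9 rule.

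Chance of meeting each threshold, with X ~ Binomial(30, p). True agreement p is an assumption:

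| True agreement p | P(X ≥ 24) | P(X ≥ 19) | P(X ≥ 20) |
|---|---|---|---|
| 65% | 0.059 | 0.655 | 0.508 |
| 80% | 0.607 | 0.991 | 0.974 |

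Patients are treated as independent; clustering within the six clinics is ignored.

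**The case against.** The strongest case on the other side has five parts.

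- **Timing is not the cause for most patients.** A reader might infer that all 30 interviews are compromised because they precede the review. The documents do not support that. For a lesion-free patient the end of the visit is the end of what that patient receives, and moving the interview would change nothing. This objection stands, and the timing point is limited to lesion patients.
- **The order is inferred.** No turnaround is stated, the workflow figure is not shown in the available copy, and section 6.2.1 places the study within routine visits. A same-visit reply cannot be excluded. Against that, the intervention is called asynchronous, findings travel by e-mail, and the provider then contacts the patient, so later feedback is the more natural reading.
- **Lesion-only enrolment.** A reader might take the photograph clause in section 5.1 to mean that only lesion patients enrol. It reads more easily as willingness to have any photograph entered, and sections 4.1, 7.1.1, 7.3.1 and 7.3.2 point the same way.
- **Acceptability is defined operationally.** The plan defines it as agreement with five statements and states the timing openly. The one item shown is a general attitude statement that needs no experience of review. This is why patients' views on remote review remain within the supported conclusion. It does not rescue the wording on satisfaction with the overall intervention. Nor does it support a claim that the result is biased in either direction, because four of the five items are not shown.
- **The criterion conflict is a different matter from timing, and its reading is not unique.** Both parts stand. The probabilities above say nothing about timing. The feasibility method concerns an average score, so the cross-reference could mean a mean item score, for which 19 and 20 of 30 are not the thresholds.

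**Conclusion.** The point holds in two limited parts.

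**Scope.** Unless replies arrive within the visit, a met criterion supports acceptability of chairside camera screening and patients' views on remote review. It does not show how patients experienced the review, the wait or the feedback. Timing is the reason only for lesion patients, a handful of 30 at the lesion frequencies assumed; for the others there is no review to experience. Providers' experience is covered by the survey and interviews, so the gap concerns patients alone. This is a matter of labelling a secondary endpoint, not a numerical error.

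**Criterion.** The two versions conflict. With the upper limit applied to the proportion of patients, results of 20 to 23 of 30 change the conclusion. At 65% true agreement the chance of declaring acceptability is about 6% under section 9, against 51% to 65% under the other rule. These figures rest on independent patients and on that reading of the cross-reference; a mean-score reading would give other thresholds.

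The plan should be corrected before results are read. Confidence is medium, because the turnaround is unstated and most interview items are unseen.

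**What to change.** 1. **One criterion.** In sections 4.2.2 and 9, use at least 80% of patients (24 of 30), with its 95% confidence interval reported beside it. Delete the sentence in 4.2.2 that refers back to the feasibility method.
2. **Narrower wording.** In sections 4.2.2 and 9, state that the endpoint is acceptability of chairside camera screening and patients' views on remote review, measured at the end of the screening visit. Use matching words in section 3.2 and section 3, item 3, so that objective and endpoint agree.
3. **Lesion status.** Link the first dummy code, already entered with lesion uploads, to the interview record. Report interview results descriptively by lesion status.

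Keep the five items and the interview timing. If replies are meant to come within the visit, say so; the wider claim would then hold only for lesion patients interviewed after the reply.

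**Cost.** The study reports a narrower conclusion. The criterion is harder to meet: 61% against 97-99% if true agreement is 80%. The lesion subgroup may hold very few patients or none. The edits are a protocol amendment, which section 12.2 requires the IRB to approve before it is implemented.

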4.2 Study Endpoints

4.2.1 Primary Study Endpoints

Feasibility will be assessed using provider surveys, semi-structured interviews, and EHR data.

Feasibility data collection.

We developed a checklist of 10 key components of the intervention based on process and will ask the dental resident and dentist subjects at the 6 FHC dental clinics if each was covered. Endorsement of 8 of the 10 checklist items (80%) by the dental provider subjects will be considered as the feasibility criterion. Specifically, we will estimate the average checklist endorsement score across all providers with its associated 95% confidence interval (CI); if the upper bound of the CI exceeds 80%, we will consider the process feasible.

Moreover, we will allow for open-ended collection of feedback on the feasibility of using the intraoral cameras for identification of oral lesions as part of the tele-mentoring intervention. Semi-structured interviews will also be conducted with dental resident subjects. We anticipate conducting 6 interviews before obtaining data saturation. The questions will be informed by the IOF and CFIR constructs and will assess specific barriers to sustaining the intervention and strategies for addressing those barriers to facilitate integration of the intervention into the routine workflow of the FHC dental clinics.

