5.6 Total Number of Subjects and Sites

All subjects will be recruited at the 6 FHC dental clinics in Brooklyn, NY.

The number of patient subjects will total 30 (5 from each of 6 FHC dental clinics).

The number of non-patient subjects will total 18: 12 dental resident and dentist subjects who will complete provider surveys (feasibility checklists), and 6 dental resident subjects who will complete semi-structured interviews.

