5.7.2 Handling of Subject Withdrawals or Termination

If a subject withdraws consent, no further data from that subject will be entered into the REDCap database for that subject. Depending on the nature of the request to withdraw, it may be necessary to remove existing data for that subject from the REDCap database.

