7.4 Safety Oversight

It is the responsibility of the Principal Investigator to oversee the safety of the study at her site. This safety monitoring will include careful assessment and appropriate reporting of adverse events as noted above, as well as the construction and implementation of a site data and safety-monitoring plan. Medical monitoring will include a regular assessment of the number and type of serious adverse events.

No DSMB will be convened for this pilot study.

8 Clinical Monitoring

Clinical site monitoring is conducted to ensure that the rights and well-being of human subjects are protected, that the reported trial data are accurate, complete, and verifiable, and that the conduct of the trial is in compliance with the currently approved protocol/amendment(s), with GCP, and with applicable regulatory requirement(s).

No independent clinical monitor will be assigned for this pilot study.

9 Statistical Considerations

Feasibility Data Analysis

Provider Survey. All quantitative analyses will be conducted by [name] under the direction of [name]. Endorsement of 8 of the 10 checklist items (80%) by the provider subjects will be considered as the feasibility criterion. Specifically, [name] will estimate the average checklist endorsement score across all dentists with its associated 95% confidence interval (CI); if the upper bound of the CI exceeds 80%, we will consider the process to be feasible.

Provider Semi-Structured Interview. All interviews will be transcribed by a transcription company and coded by 2 research staff members ([name] and [name]). The research staff members will code individually and then meet to discuss and agree upon the final codes. The analysis of the qualitative data will utilize the techniques of narrative analysis and be guided by the constant comparison analytic approach to identify themes.

Acceptability Data Analysis

Patient Exit Survey. The acceptability criterion of the intervention will be that 80% or more of patients rate all 5 administered acceptability questions as “strongly agree” or “agree” on a Likert Scale.

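### The acceptability endpoint has two possible pass rules: at least 80% of patients (24 of 30), or an upper 95% confidence bound above 80% (from 19 or 20 of 30)

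*Combined protocol and SAP*

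**What the plan says.** Section 4.2.2 sets the threshold: "The acceptability criterion of the intervention will be that 80% or more of patients rate all five administered acceptability questions as" agree or strongly agree. It then adds "We will evaluate acceptability as described above for feasibility".

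The evaluation it points to is in section 4.2.1: "we will estimate the average checklist endorsement score across all providers with its associated 95% confidence interval (CI"), followed by the decision rule "if the upper bound of the CI exceeds 80%, we will consider the process feasible".

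Section 9, under Acceptability Data Analysis, gives the threshold again, "The acceptability criterion of the intervention will be that 80% or more of patients rate all 5 administered acceptability questions" as agree or strongly agree, with no interval and no cross-reference. For the provider survey, the same section does repeat the upper-bound rule.

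On numbers, section 5.6 states "The number of patient subjects will total 30 (5 from each of 6 FHC dental clinics"). Section 9.1 says that no sample size calculation is made. Section 5.7.2 allows that after a withdrawal "it may be necessary to remove existing data for that subject from the REDCap database", so the denominator may be below 30.

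**The concern.** Taken literally, section 4.2.2 states a threshold and then adopts a test that passes results below it. An upper confidence limit lies above the observed proportion, so with 30 patients it can exceed 80% when the observed rate is well under 80%. Section 9 does not resolve this, because it is silent on the interval and does not withdraw the cross-reference.

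The sentence has other readings. It could ask only for an interval to be reported. It could also mean an interval on an average agreement score, since section 4.2.1 describes an interval for a mean checklist score and not for a proportion of patients. Neither the interval method nor its sidedness is given.

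At stake is the verdict on the only secondary objective (section 3.2). For a middle range of results that verdict depends on how one sentence is read, and the reading could be settled after the data are known. Section 3 makes scale-up conditional on the pilot proving successful, so the verdict may be used.

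**Working it through.** **Inputs.** Patients: 5 × 6 = 30 (section 5.6), which reproduces the plan's figure; the plan gives no power or operating characteristics to reproduce. Threshold: 80% (sections 4.2.2 and 9). Confidence level: 95% (section 4.2.1). Assumptions: one yes/no result per patient (agrees with all five statements), all 30 evaluable, two-sided interval, independent patients.

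**Step 1: stated criterion.** 0.80 × 30 = 24, so at least 24 patients must agree with all five.

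**Step 2: upper-bound rule.** Find the smallest x for which the upper limit for x/30 exceeds 0.80.

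- Wald: p + 1.96 × √(p(1 − p)/n). At x = 19, 0.6333 + 1.96 × √(0.6333 × 0.3667/30) = 0.6333 + 0.1724 = 0.806, a pass.
- Wilson: [p + z²/(2n) + z√(p(1 − p)/n + z²/(4n²))]/(1 + z²/n). At x = 20, (0.6667 + 0.0640 + 0.1804)/1.1281 = 0.808, a pass. At x = 19 it is 0.781, a fail.

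| Agree with all five | Observed | Wald upper | Wilson upper | Clopper-Pearson upper | Meets 80%? |
|---|---|---|---|---|---|
| 18 | 60.0% | 0.775 | 0.754 | 0.773 | no |
| 19 | 63.3% | 0.806 | 0.781 | 0.801 | no |
| 20 | 66.7% | 0.835 | 0.808 | 0.827 | no |
| 21 | 70.0% | 0.864 | 0.833 | 0.853 | no |
| 22 | 73.3% | 0.892 | 0.858 | 0.877 | no |
| 23 | 76.7% | 0.918 | 0.882 | 0.901 | no |
| 24 | 80.0% | 0.943 | 0.905 | 0.923 | yes |

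Agresti-Coull (0.809) and Jeffreys (0.814) also first pass at 20. A t-based interval for the mean of the yes/no results passes at 19 (0.816). So 20 to 23 passes the upper-bound rule under every two-sided method tried and misses the stated criterion. With a one-sided 95% limit the cutoff is 20 (Wald, Clopper-Pearson) or 21 (Wilson), so the conflict remains at 21 to 23.

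**Step 3: how often the verdicts differ.** Exact binomial, n = 30, cutoff 20 against cutoff 24. The rules disagree when 20 ≤ X ≤ 23.

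| True rate | P(X ≥ 20) | P(X ≥ 24) | Disagree |
|---|---|---|---|
| 65% | 0.508 | 0.059 | 45% |
| 70% | 0.730 | 0.160 | 57% |
| 75% | 0.894 | 0.348 | 55% |
| 80% | 0.974 | 0.607 | 37% |
| 85% | – | – | 15% |
| 90% | – | 0.974 | 2.6% |

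At a true 70%, P(pass) is 0.841 with cutoff 19 and 0.589 with cutoff 21.

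**Step 4: sensitivity.** Clustering by clinic, as a beta-binomial with 6 clinics of 5 and a true rate of 70%, gives 0.714 against 0.184 at an assumed intraclass correlation of 0.05, and 0.702 against 0.205 at 0.10. With 28 evaluable patients (illustrative), 0.80 × 28 = 22.4, so the criterion needs 23; the two-sided upper-bound rule passes from 18 or 19.

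**The case against.** The best defence is that the two rules need not collide. The feasibility rule concerns a mean of provider checklist scores, while acceptability is a proportion of patients, so the rule cannot be carried over without adaptation. If the cross-reference only asks for an estimate with an interval, there is no conflict and the 20-to-23 range does not arise. Section 9 is the statistical section. It spells out the upper-bound rule for providers and gives patients the plain 80% criterion, which suggests that 24 of 30 is what is meant. This is also a secondary objective in a pilot, and if nearly all patients agree, both rules give the same answer.

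Much of this is fair. The figures above measure one reading, and disagreement falls to 15% at a true 85% and 2.6% at 90%; the documents give no expected rate. But the defence shows only that a better reading exists. Section 4.2.1 introduces the upper-bound rule as the specific test of its own 80% criterion, so carrying that test over is a natural reading of section 4.2.2. No text ranks section 9 above section 4.2.2, and silence in section 9 does not cancel the cross-reference. Pilot status excuses the missing sample size calculation; it does not excuse a pass/fail criterion that can give two answers to the same data.

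Whether an upper-bound rule suits the primary feasibility endpoint is a separate question. This point is confined to acceptability.

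**Conclusion.** The concern holds. The plan does not determine which rule decides acceptability, and the literal reading of section 4.2.2 contradicts the threshold in the sentence before it. The gap is four to five patients out of 30: a cutoff of 24 against 20 or 19. Acceptability could be declared with about two-thirds of patients, or slightly fewer, agreeing with all five statements.

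The exact cutoffs rest on a yes/no result per patient, 30 evaluable patients and a two-sided interval. The conflict survives the choice of interval method, a one-sided limit, modest clustering and a small loss of patients. Its practical weight is greatest if true agreement is about 65% to 80% and slight from 90% upward. It should be fixed before the data are seen; it has no bearing on patient safety.

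**What to change.** Delete the cross-reference in section 4.2.2 and put one identical rule in sections 4.2.2 and 9, for example:

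> The intervention will be considered acceptable if the observed proportion of evaluable patients who agree or strongly agree with all five statements is at least 80% (24 if all 30 are evaluable). The exact (Clopper-Pearson) 95% confidence interval will be reported for precision only and will not be used as the pass rule.

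This keeps the one criterion that both sections already share and covers withdrawals. The choice of exact interval is a convention; another named method would serve.

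The change needs no extra data, but the bar is stricter than under the upper-bound reading (cutoff 24 against 20). The pass probability falls from 97% to 61% at a true 80%, and from 89% to 35% at a true 75%; at a true 90% it is still 97%. Acceptability and feasibility would also have different forms of decision rule unless section 4.2.1 is changed too. If the sponsor prefers the more lenient rule, it should say so explicitly in both sections, with the interval method and sidedness, before the data are seen.
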